15.1.1 All Adverse Events

All AEs recorded during the course of the trial (i.e. assessed from signature of informed consent until the end of treatment/safety follow-up visit) will be coded according to MedDRA latest version and assigned to a SOC and PT.

TEAEs will be summarized by worst severity, using MedDRA latest version PT as event category and MedDRA primary SOC body term as Body System category. The severity of AEs will be assessed by the investigator per the Qualitative Toxicity Scale as detailed in the study protocol: mild, moderate, severe.

TEAEs related to trial treatment are those events with relationship related, or missing, or unknown.

The following will be summarized in an overview table with the number and percentage of participants (and the number of events) by treatment and overall:

- Any TEAEs
- Any trial treatment-related TEAEs
- Any serious TEAEs
- Any trial treatment-related serious TEAEs
- Any severe TEAE
- Any trial treatment-related severe TEAEs
- Any TEAEs leading to death
- Any trial treatment-related TEAEs leading to death

TEAEs will be summarized by treatment and total T, total R and overall in tables with:

- The number and percentage of participants by treatment with at least one TEAE and the number of events overall and by SOC and PT. SOC terms will be sorted alphabetically and PTs within each SOC term will be sorted by descending overall frequency.
- The number and percentage of participants by treatment with at least one non-serious TEAE and the number of non-serious TEAE applying frequency threshold of 5% according to SOC (i.e. SOC events with frequency > 5% in any arm). SOC terms will be sorted alphabetically and PTs within each SOC term will be sorted by descending overall frequency.

In addition the following tables will be provided. SOC terms will be sorted alphabetically and PTs within each SOC term will be sorted by descending frequency (based on all treatment groups combined):

- A table by severity of TEAEs with the number and percentage of participants by treatment with at least one TEAE and the number of events by SOC and PT.
- A table by relationship to trial treatment with the number and percentage of participants by treatment with at least one TEAE and the number of events by SOC and PT.

Pre-treatment AEs (AEs with onset after informed consent but before start of treatment) and TEAEs will be listed separately.

15.1.2 Adverse Events Leading to Treatment Discontinuation

TEAEs leading to permanent discontinuation of trial treatment will be summarized by treatment and overall including number of participants, percentage and number of events.

A listing of TEAEs leading to permanent discontinuation of a trial treatment will additionally be provided.

15.2 Deaths, Other Serious Adverse Events, and Other Significant Adverse Events

15.2.1 Deaths

All deaths as well as reason for death will be based on information from the “Report of Participant Death” CRFs.

Listing of deaths, if any, will be provided displaying date and cause of death (including TEAE leading to death and relatedness to trial treatment, when applicable), and date and time of treatment administration.

15.2.2 Serious Adverse Events

A summary table of serious adverse events (SAEs), if any, by treatment and overall will be provided displaying the number and percentage of participants by treatment with at least one SAE and the number of SAEs overall and by SOC and PT. SOC terms and PTs within each SOC term will be sorted alphabetically.

Listing of SAEs, if any, will be provided in addition.

15.3 Clinical Laboratory Evaluation

All laboratory data will be reported with SI units. Laboratory parameters will be listed by participant and treatment T1, T2, R1, R2 and time-point and summarized indicating the treatment

T and R at the respective time-point using descriptive statistics for absolute values and change from baseline (period-baseline) over time.

Laboratory values that are outside the normal range will also be flagged in the data listings, along with corresponding normal ranges. Any out-of-range values will additionally be listed separately.

See Appendix 5 of the CSP for a table of the safety laboratory evaluations.

Safety laboratory values are separated into:

- Hematology
- Biochemistry
- Urinalysis
- Other tests

Summary tables will be produced for the groups Hematology and Biochemistry.

15.4 Vital Signs

Vital signs will be listed by participant and time-point and summarized for absolute values and changes-from-baseline (period-baseline) by time point and treatment T1, T2, R1 and R2 using descriptive statistics. Descriptive statistics tables will start at baseline.

15.5 ECG Evaluation

ECG data will be listed by participant and time-point and summarized by absolute values and changes-from-baseline (period-baseline) by treatment T1, T2, R1 and R2 using descriptive statistics. Descriptive statistics tables will start at baseline. Clinically significant ECG findings for individual participants will be listed and summarized.

The time intervals (PR, QRS, RR, QT and corrected QT intervals [based on Fridericia's formula, QTcF]) will be summarized descriptively by treatment.

The Fridericia's Correction (QTcF) is derived as follows:

$$\text{Fridericia's Correction (QTcF)} \quad QTc_f = \frac{QT}{\sqrt[3]{RR}}$$

where: RR = RR-interval measured in seconds.

Observed QTcF values will be categorized according to their absolute values into the categories

- ≤ 430 ms,
- > 430 and ≤ 450 ms,
- > 450 and ≤ 480 ms,
- > 480 and ≤ 500 ms, and
- > 500 ms,

and categorized according to their absolute change from period baseline into the categories

- ≤ 30 ms,
- > 30 and ≤ 60 ms, and
- > 60 ms.

The number and percentage of participants by these categories at any post-dose assessment will be tabulated by treatment T1, T2, R1 and R2. All ECG measurements and changes from period baseline will be listed, with abnormalities (as reported of the investigator on the ECG eCRF page) indicated.

Investigator reported interpretation results will also be tabulated by treatment T1, T2, R1 and R2 using the number and percentage of participants for each interpretation category (Normal, Abnormal Not Clinically Significant [NCS], Abnormal Clinically Significant [CS]).

16 Analyses of Other Endpoints

16.1 Pharmacokinetics

General Specifications for Plasma Concentration Data

PK evaluation will be performed by the Clinical PK/PD Group, Merck Healthcare KGaA, Darmstadt, Germany, or by a CRO selected by the Sponsor.

Concentrations of rac-PZQ, R-(-)-PZQ and S-(+)-PZQ in plasma will be presented in tables and descriptively summarized by treatment T1, T2, R1, R2 and nominal time point using number of observations (n), Mean, SD, standard error of the mean (SEM), median, Min, Max, and CV%. Descriptive statistics of concentration data will be calculated using values with the same precision as the source data, and rounded for reporting purposes only. The following conventions will be applied when reporting descriptive statistics of PK concentration data:

Mean, Min, Median, Max:	3 significant digits
SD, SEM:	4 significant digits
CV%:	1 decimal place

Values below the lower limit of quantification of the assay (LLOQ) will be taken as zero for summary statistics of PK concentration data. Missing concentrations (e.g., no sample, insufficient sample volume for analysis, no result, or result not valid) will be reported and used generally as “no result” (“N.R.”). Pre-dose samples that occur before the first drug

administration will be assigned a time of 0 hours, as if the sample had been taken simultaneously with the study drug administration.

All available concentration data will be listed. Data of participants not in the PK analysis set or invalid data will be flagged accordingly. Any flags will be included in SDTM and ADaM, respectively.

General Specifications for PK Parameter Data

PK parameter data will be descriptively summarized: n, Mean, SEM, SD, CV%, Min, median, Max, geometric mean (GeoMean), the geometric coefficient of variation (GeoCV%) and the 95% confidence interval (CI) for the GeoMean (LCI 95% GM, UCI 95% GM).

PK parameter C_{max} will be reported with the same precision as the source data. All other PK parameters will be reported to 3 significant figures. In export datasets, as well as in the SDTM PP domain, PK parameters will be provided with full precision, and will not be rounded. Descriptive statistics of PK parameter data will be calculated using full precision values, and rounded for reporting purposes only.

The following conventions will be applied when reporting descriptive/inferential statistics of PK parameter data:

Mean, Min, Median, Max, GeoMean, 95% CI:	3 significant digits
SD, SEM:	4 significant digits
CV%, GeoCV%:	1 decimal place
Ratio of GeoMean (in %) and 95% CI	2 decimal places

To ensure a reliable estimate of the extent of exposure, AUC_{extra} should be less than or equal to 20%. If AUC_{extra} is greater than 20%, all parameters derived using λ_z (i.e. λ_z , $t_{1/2}$, $AUC_{0-\infty}$, AUC_{extra} , V_z/f , CL/F) will be listed, but set to missing for the calculation of descriptive statistics.

All statistical analyses and descriptive summaries of pharmacokinetic data will be performed on the PK Analysis Set. All available data will be listed. Data of participants not in the PK analysis set or invalid data will be flagged accordingly. Any flags will be included in SDTM and ADaM, respectively.

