Estimates and confidence intervals will be back-transformed to the natural scale. Bioequivalence will be accepted if, firstly, the back-transformed 90% confidence intervals are included in the acceptance range, and, secondly, the geometric mean ratios are contained in the conventional acceptance range 80.00% to 125.00%.

The estimated within-subject variability  $CV_{WR}$  may be inflated in the presence of outliers. In order to exclude such inflation, sensitivity analyses will be performed. In these analyses, outliers will be identified using graphical methods (such as plotting the PK parameter after the first administration against the corresponding value after the second administration) and/or statistical methods (such as identifying subjects whose studentized residuals fall outside the interquartile range), and the acceptance range will be based on  $CV_{WR}$  calculated with outliers removed from the dataset.

Descriptive statistics and boxplots for PK parameters of all analytes will be provided by treatment. Additional exploratory analyses will be described in the integrated analysis plan.

PK analyses will be specified in the Integrated Analysis Plan finalized before database lock.

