6.2 Final Analysis

The final, planned analyses identified in the CSP and in this IAP will be performed after the last participant has completed the last visit, i.e. end of treatment/safety follow-up visit with all trial data in-house, all data queries resolved, and the database locked.

A data review meeting will be held prior to database lock for the final analysis. In addition, no database can be locked until this IAP has been approved.

7 Changes to the Planned Analyses in the Clinical Study Protocol

There are no changes to the planned analyses in the CSP.

8 Protocol Deviations and Analysis Sets

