An analysis of variance (ANOVA) with treatment, period, sequence and subject within sequence as fixed effects, will be fitted to log-transformed PK parameters AUC_{0-t} and C_{\max} according to Method A in Question 8 in [EMA/618604/2008 Rev. 13](#). Only participants with at least one valid PK parameter under both reference and test treatment will be included in this model. Least-squares mean differences between treatments will be derived on the log-scale together with 90% confidence intervals.

Estimates and confidence intervals will be back-transformed to the natural scale. Bioequivalence will be accepted if, firstly, the back-transformed 90% confidence intervals are included in the acceptance range, and, secondly, the geometric mean ratios are contained in the conventional acceptance range 80.00% to 125.00%.

The estimated within-subject variability CV_{WR} may be inflated in the presence of outliers. In order to exclude such inflation, sensitivity analyses will be performed. In these analyses, outliers will be identified using graphical methods by plotting the PK parameter after the first administration (R1) against the corresponding value after the second administration (R2), and/or statistical methods (such as identifying subjects whose studentized residuals fall outside the

interquartile range and/or outside the whiskers), and the acceptance range will be based on CV_{WR} calculated with outliers removed from the dataset.

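### Does the 95% CI label on the ratio of geometric means in the SAP's rounding conventions put the 90% bioequivalence interval in doubt?

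*SAP*

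**What the plan says.** SAP Section 16.1, under the general specifications for PK parameter data, introduces a short list of rounding rules: "The following conventions will be applied when reporting descriptive/inferential statistics of PK parameter data". Two rows mention a confidence interval. The first, "Mean, Min, Median, Max, GeoMean, 95% CI", is given to 3 significant digits. The second, "Ratio of GeoMean (in %) and 95% CI", is given to 2 decimal places.

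The same part of the SAP plans a 95% interval for one quantity only, the geometric mean of a single treatment: "the 95% confidence interval (CI) for the GeoMean (LCI 95% GM, UCI 95% GM".

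The treatment comparison is defined in SAP Section 16.1.1: "Least-squares mean differences between treatments will be derived on the log-scale together with 90% confidence intervals". The decision rule follows in the same section: "Bioequivalence will be accepted if, firstly, the back-transformed 90% confidence intervals are included in the acceptance range". Protocol Section 9.4.3 specifies the same model and rests the decision on the same interval: "the back-transformed 90% confidence intervals are included in the acceptance range". SAP Section 7 says of any departure from the protocol: "There are no changes to the planned analyses in the CSP".

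**The concern.** The ratio of geometric means is the primary result of the trial, and its interval is what is compared with the acceptance range. A plan that gives two confidence levels for that interval, 95% in one place and 90% in another, appears to leave the central output ambiguous.

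The usual harmless explanations do not remove the mismatch. The row cannot refer to the interval for a single-treatment geometric mean, because that has its own row at a different precision. It is not confined to descriptive output, because the list covers inferential statistics as well. It is not a declared change, because the SAP declares none.

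A 90% two-sided interval corresponds to one-sided tests at 0.05 and a 95% interval to tests at 0.025. If the 95% interval were used for the decision, the criterion would be stricter than planned. If it were only printed, a reader could see an interval crossing a limit in a study that had met its criterion. The opposite slip is also possible: a 90% interval printed under a 95% heading, which would overstate its confidence level.

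**Working it through.** **Where each level applies**

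| Place | Quantity | Level | Role |
|---|---|---|---|
| SAP 16.1, first row with an interval | Geometric mean | 95% | Rounding, 3 significant digits |
| SAP 16.1, second row with an interval | Ratio of geometric means | 95% | Rounding, 2 decimals |
| SAP 16.1.1, model | Test/reference difference on log scale | 90% | Analysis |
| SAP 16.1.1, decision | Back-transformed interval | 90% | Bioequivalence rule |
| Protocol 9.4.3, model and decision | Same as SAP 16.1.1 | 90% | Analysis and rule |

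Only the second row is out of line. Every place that says what to compute or how to decide uses 90%.

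**Inputs for the size of a display error**

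- 32 evaluable participants (protocol Section 7.2; SAP Section 10).
- Within-subject CV of the reference in the first bioequivalence study: Cmax 47.08%, AUC 33.4% (protocol Section 4.2.2).
- Scaling constant 0.760 (protocol Section 9.4.3; SAP Section 16.1.1).
- Assumed: all four periods complete, and equal within-subject variances for test and reference.

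**The plan's own limits reproduce.** With s = sqrt(ln(1 + CV²)), a CV of 50% gives s = 0.4724. Then exp(∓0.760 × 0.4724) gives 69.84% to 143.19%, the fixed range stated in both documents.

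**Scaled limits at the earlier study's CVs**

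- AUC: s = 0.3252, limits 78.10% to 128.04%.
- Cmax: s = 0.4474, limits 71.17% to 140.50%.

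**Standard error and quantiles.** For a balanced two-sequence, four-period full replicate, SE = s/√32, which is 0.0575 for AUC and 0.0791 for Cmax. The residual df are 3 × 32 − 4 = 92. The t quantiles are 1.6616 for a 90% interval and 1.9861 for a 95% interval, so the width ratio on the log scale is 1.9861/1.6616 = 1.195.

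**Intervals, ratio × exp(∓t × SE)**

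| Endpoint | Observed ratio | 90% CI | 95% CI | Limits |
|---|---|---|---|---|
| AUC | 100% | 90.89–110.02 | 89.21–112.10 | 78.10–128.04 |
| AUC | 115% | 104.52–126.53 | 102.59–128.91 | 78.10–128.04 |
| Cmax | 100% | 87.68–114.05 | 85.46–117.01 | 71.17–140.50 |
| Cmax | 122% | 106.97–139.14 | 104.26–142.75 | 71.17–140.50 |

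At 100% the two levels tell the same story. At 115% (AUC) and 122% (Cmax) the 90% interval is inside the limits and the 95% interval crosses the upper one. Those two ratios were picked because they fall where the levels disagree. The full bands of disagreement are 85.93–87.55% and 114.22–116.37% for AUC, and 81.17–83.28% and 120.08–123.20% for Cmax.

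**How often a result would land there.** On the log scale the upper band starts at 0.760 × √32 − 1.9861 = 2.313 standard errors above a ratio of 100% and ends at 0.760 × √32 − 1.6616 = 2.638. This holds for both endpoints because s cancels. Treating the CVs as fixed and using the normal distribution, the two bands together hold about 1.2% of results per endpoint when the true ratio is 100%. At a true ratio of 95% or 105% the figure is about 3.5–3.8% for AUC and 2.4–2.6% for Cmax. At 90% or 110% it is about 9–11% and 6–7%. In all these cases only the printed interval would differ; the decision is made on the 90% interval.

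**The case for a change.** The best case for acting is that this row governs the display of the primary result. The acceptance limits are stated to two decimals, so the convention for the interval compared with them ought to name the right interval. Read literally, the SAP assigns two decimals to an interval nobody planned and says nothing about the one that decides bioequivalence. Correcting it would cost one word.

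Part of this stands: the label is wrong, and no reading of the text makes it right. The claim that the 90% interval has no reporting precision does not stand. Once the label is recognised as a slip, the row is the precision rule for the ratio and its interval, and two decimals match the way the limits are written.

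The route from the label to a misleading table is also conjectural. SAP Section 18 lists no appendices, and the documents contain no table shells. The PK parameter tables listed in Section 16.1.1 are summaries by treatment administration. Anyone programming the bioequivalence output has to take the model, the back-transformation and the acceptance rule from Section 16.1.1, which states 90% at each step.

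Printing a true 95% interval could suggest a failure but not a false claim of equivalence. Mislabelling a 90% interval is not conservative in that sense, but it does not alter the decision either.

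**Conclusion.** The inconsistency is real and clerical. One label in a list of rounding rules disagrees with the only interval planned for the ratio. The protocol and the SAP's analysis section both set that interval at 90% and use it for the decision. A specific analysis section takes precedence over a label in a decimals table, and no competent analyst would be left unsure which interval decides bioequivalence.

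Nothing inferential turns on the label: the test, its error rate, the power, the sample size and the conclusion are the same with or without it. The most it could do is affect a printed interval. A true 95% interval would be 1.195 times as wide on the log scale (32 participants, df 92, complete data), and it would look different from the decision interval only in narrow ranges of the observed ratio. The interval and band figures also rest on the earlier study's CVs and on equal test and reference variances. The conclusion rests on the text alone and needs none of those assumptions. No change to the plan follows.

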### 3 Objectives and Endpoints

Objectives	Endpoints (Outcome Measures)
Primary	
To assess the BE of the 600 mg coated Cesol tablet versus the comparator 600 mg tablet of Biltricide at a dose of 1200 mg with regard to rac-PZQ	PK parameters $C_{max}$ and area under the plasma concentration-time curve from time zero to last measurable concentration-(AUC 0-t ) of rac-PZQ after single dose administration
Secondary	
To evaluate the safety and tolerability of the 600 mg coated Cesol tablet versus the comparator 600 mg tablet of Biltricide at a dose of 1200 mg	Occurrence of TEAEs and treatment related AEs per Qualitative Toxicity Scale Standard laboratory hematology and biochemical parameters, vital signs (body temperature, systolic and diastolic blood pressure, and pulse rate) and ECG parameters.
To assess the BE of the 600 mg coated Cesol tablet versus the comparator 600 mg tablet of Biltricide at a dose of 1200 mg with regard to PZQ enantiomers	PK parameters $C_{max}$ and area under the plasma concentration-time curve from time zero to last measurable concentration (AUC 0-t ) of R-(-)-PZQ and S-(+)-PZQ after single dose administration
To further characterize the PK profile of the 600 mg coated Cesol tablet versus the comparator 600 mg tablet of Biltricide at a dose of 1200 mg	PK parameters of rac-PZQ, R-(-)-PZQ and S-(+)-PZQ after single dosing: AUC 0-∞ , time to reach maximum plasma concentration ( $t_{max}$ ), $t_{lag}$ , $t_{1/2}$ , $\lambda_z$ , CL/f and $V_z/f$

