### 9.4 Statistical Analyses

Statistical analysis will be performed using the computer program package SAS® System (release 9.2 or later version; SAS Institute, Cary NC, USA). Details on the statistical analysis will be presented in the integrated analysis plan prior to database lock.

The statistical analysis will not be started until all data have been corrected and checked for plausibility, and until all necessary coding and assessments have been completed.

Medical history and AE terms will be coded with the latest version of the Medical Dictionary for Regulatory Activities (MedDRA; version 22.0 or later); concomitant medication will be coded with WHO Drug Dictionary, WHO Drug Reference List and Anatomical Therapeutic Chemical Classification System, latest version. Versions of dictionaries used for coding will be defined in the Data Management Plan (DMP).

All data recorded during the study will be presented in individual data listings.

All data will be evaluated as observed, no imputation method for missing values will be used except for missing dates/times in AE data which will be performed for the classification of treatment-emergence, assigning AEs to treatment periods and for calculation of duration. The handling of concentration values below the limit of quantification will be described in the statistical analysis plan.

Summary statistics will be provided for all endpoints.

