16.1.1 Planned Analyses of PK Parameter Data

The following PK parameter tables will be produced:

- Summary of PK parameters by treatment T1, T2, R1 and R2 of all analytes.

The following listing will be produced:

- Individual PK parameters listed by treatment T1, T2, R1, R2. Excluded PK parameters will be flagged.

The following figures will be produced for PK parameters:

- Boxplots for the C_{\max} and AUC_{0-t} by treatment T1, T2, R1, R2 of all analytes.

The analysis of the primary endpoints AUC_{0-t} and C_{\max} of rac-PZQ will be performed using the PK population. The analysis of the secondary endpoints AUC_{0-t} and C_{\max} of R-(-)-PZQ and S-(+)-PZQ will use a similar approach.

For the analysis of AUC_{0-t} and C_{\max} , a reference-scaled BE approach will be applied as follows:

The within-subject variability of the reference product will be calculated from a linear model fitted to the log-transformed PK parameters C_{\max} and AUC_{0-t} , obtained under reference treatment only, with sequence, subject within sequence, period included as fixed effects, described in Section 3.4 of Question 8 in [EMA/618604/2008 Rev. 13: Questions & Answers](#): positions on specific questions addressed to the Pharmacokinetics Working Party (PKWP). In this analysis, only participants with evaluable data from both administrations of the reference product will be included. If the within-subject coefficient of variation for the reference treatment ($CV_{WR} \leq 30\%$ for C_{\max} or AUC_{0-t} (i.e. the within-subject CV for the reference drug is $\leq 30\%$), then the common acceptance range (80.00% to 125.00%) for BE will apply for the respective PK parameter. For $30\% < CV_{WR} \leq 50\%$ the acceptance interval will be widened according to $[L, U] = \exp(\mp k s_{WR})$, where U is the upper limit of the acceptance range, L is the lower limit of the acceptance range, k is the regulatory constant set to 0.760 and s_{WR} is the intrasubject standard deviation of the log-transformed values of C_{\max} or AUC_{0-t} of the reference product, and $CV_{WR} = \sqrt{\exp(s_{WR}^2) - 1}$. s_{WR} will be calculated using the data under reference treatment only. For all values of CV_{WR} greater than 50% the acceptance range is fixed to [69.84% to 143.19%].

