16.1.3 Estimation of Individual PK Parameters

The following non-compartmental PK parameters will be calculated from the individual plasma rac-PZQ, R-(-)-PZQ and S-(+)-PZQ concentration-time data using commercial software Phoenix[®]/WinNonlin[®] (Version 6.3 or higher) at PPD. C_{max} and AUC_{0-t} are the main parameters for further statistical analysis.

Symbol	Definition
AUC_{0-t}	The area under the concentration-time curve (AUC) from time zero (= dosing time) to the last sampling time (t_{last}) at which the concentration is at or above the lower limit of quantification. Calculated using the mixed log-linear trapezoidal rule (linear up, log down).

Symbol	Definition
$AUC_{0-\infty}$	The AUC from time zero (dosing time) extrapolated to infinity, based on the predicted value for the concentration at t_{last} , as estimated using the linear regression from λ_z determination. $AUC_{0-\infty} = AUC_{0-t} + C_{last\ pred} / \lambda_z$.
$AUC_{extra\%}$	The AUC from time t_{last} extrapolated to infinity given as percentage of $AUC_{0-\infty}$. $AUC_{extra\%} = (\text{extrapolated area}/AUC_{0-\infty}) * 100$. The predicted $AUC_{0-\infty}$ should be used.
CL/f	The apparent oral clearance. $CL/f = \text{Dose}_{p.o.} / AUC_{0-\infty}$. The predicted $AUC_{0-\infty}$ should be used.
C_{max}	Maximum observed concentration.
$t_{1/2}$	Apparent terminal half-life. $t_{1/2} = \ln(2) / \lambda_z$.
t_{lag}	The time prior to the first measurable (non zero) concentration.
t_{max}	The time to reach the maximum observed concentration collected during a dosing interval (i.e., 1 st occurrence in case of multiple/identical C_{max} values).
V_z/f	The apparent volume of distribution during the terminal phase following extravascular administration. $V_z/f = \text{Dose} / (AUC_{0-\infty} * \lambda_z)$ following single dose.
λ_z	Terminal first order (elimination) rate constant. Determined from the terminal slope of the log-transformed concentration curve using linear regression on terminal data points of the curve.

The following PK parameters will be calculated for diagnostic purposes and listed, but will not be summarized:

- First ($\lambda_{z\ low}$) and last ($\lambda_{z\ upp}$) time point of the time interval of the log-linear regression to determine λ_z .
- Number of data points (N_λ) included in the log-linear regression analysis to determine λ_z .
- Goodness of fit statistic (adjusted Rsq) for calculation of λ_z .

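### The SAP's 20% rule removes %AUCextra from its own summary, so the table that checks the 12 h sampling window cannot show a failure (minor; descriptive endpoints only)

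*SAP*

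**What the plan says.** SAP 16.1 (General Specifications for PK Parameter Data) gives the criterion and its reason: "To ensure a reliable estimate of the extent of exposure, AUC_{extra} should be less than or equal to 20" per cent. Above that limit, λz, t1/2, AUC0-∞, AUCextra, Vz/f and CL/F "will be listed, but set to missing for the calculation of descriptive statistics".

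SAP 16.1.1 plans a "Summary of PK parameters by treatment T1, T2, R1 and R2 of all analytes". SAP 16.1.3 has a separate group introduced by "The following PK parameters will be calculated for diagnostic purposes and listed, but will not be summarized". That group holds only the λz time limits, the number of regression points and the adjusted R². %AUCextra is not in it, so it belongs in the summary table.

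SAP 16.1 applies one set of statistics to PK parameters without exception. It includes n, mean, SD, min, median and max, and also "geometric mean (GeoMean), the geometric coefficient of variation (GeoCV%) and the 95% confidence interval (CI) for the GeoMean". For tlag, SAP 16.1.3 has "The time prior to the first measurable (non zero) concentration". Table 3 in Protocol 8.5 adds that it is the last time point below LLOQ before the first quantifiable one.

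Protocol 3 names AUC0-∞, tmax, tlag, t1/2, λz, CL/f and Vz/f as endpoints for the objective "To further characterize the PK profile of the 600 mg coated Cesol tablet versus the comparator 600 mg tablet of Biltricide". Protocol 9.4 states "Summary statistics will be provided for all endpoints" and contains no 20% rule.

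**The concern.** %AUCextra measures how much of the exposure lies beyond the 12 h sample, so it shows whether sampling was long enough. A rule that deletes every value above 20% from that measure's own summary is circular: the table will look satisfactory whether no profiles fail or many do.

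The deletion is also not random with respect to the other parameters. A profile exceeds 20% because elimination is slow, absorption is late, or both. Removing such profiles from the t1/2, AUC0-∞ and CL/f summaries moves each in a known direction. If the share removed differed between the coated test tablet and the reference, the descriptive comparison in the third secondary objective would be made on differently selected sets.

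tlag is a smaller matter in the same section. A geometric mean needs positive values, and tlag can be zero.

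**Working it through.** The documents give no expected %AUCextra, exclusion rate or half-life variability, so there is no stated figure to reproduce.

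**The cap.** This needs no assumption. Every value above 20% is removed and %AUCextra is among the summarised parameters, so the printed maximum is at most 20%.

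**Inputs from the documents.** Mean half-life of rac-PZQ 2.5 h (Protocol 4.2.3); last sample at 12 h (Protocol 8.5).

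**Assumptions.** One-compartment model, absorption rate ka 0.7 to 3 /h, log-normal half-life with median 2.5 h and CV 30% or 60%.

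**Formulas.** With ke = ln 2 / t1/2,

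%AUCextra = 100 × (ka·e^(-12ke) - ke·e^(-12ka)) / (ka - ke).

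Solving for 20% gives a trigger half-life h. With s = √ln(1 + CV²) and z = ln(h/2.5)/s, the share removed is 1 - Φ(z), and the geometric mean of what remains is multiplied by exp(-s·φ(z)/Φ(z)).

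Example, ka 0.7 and CV 60%: h = 4.47 h, s = 0.555, z = 1.05. Share removed = 14.7%; factor = exp(-0.555 × 0.230/0.853) = 0.861, that is -13.9%.

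| ka (/h) | %AUCextra at t1/2 2.5 h | trigger h (h) | CV 30%: removed; GeoMean t1/2 | CV 60%: removed; GeoMean t1/2 |
|---|---|---|---|---|
| 0.7 | 5.9 | 4.47 | 2.4%; -1.7% | 14.7%; -13.9% |
| 1 | 5.0 | 4.70 | 1.6%; -1.2% | 12.8%; -12.4% |
| 1.5 | 4.4 | 4.87 | 1.2%; -0.9% | 11.5%; -11.4% |
| 3 | 4.0 | 5.02 | 0.9%; -0.7% | 10.4%; -10.6% |

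If V/f is independent of half-life, AUC0-∞ shifts by the same percentage and CL/f by the reciprocal: from 1/0.993 (+0.7%) to 1/0.861 (+16%).

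**Sensitivity to late absorption.** Take a mono-exponential decline after an effective input time T0: %AUCextra = 100 × 2^(-(12-T0)/t1/2), which exceeds 20% when t1/2 > (12-T0)/log2(5). At t1/2 2.5 h this gives 3.6%, 8.2% and 14.4% for T0 of 0, 3 and 5 h, with triggers of 5.17, 3.88 and 3.01 h. In a simulation with median T0 3 h (CV 30%) and half-life CV 30%, 9.2% of profiles are removed, about 3 of 36 per administration. Mean %AUCextra is then 10.1% on all profiles against 8.5% under the rule, and geometric mean t1/2 is 2.38 h against 2.50 h. Over half-life CV 20% to 60% and median T0 2 to 5 h, the share removed runs from 0.6% to 41% and the t1/2 shift from -0.3% to -28%. A range this wide shows that the documents do not fix the size.

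**tlag.** The predose sample is assigned time 0 (SAP 16.1). If the 0.25 h sample is quantifiable, the last time below LLOQ is predose and tlag = 0, whose log is undefined. Invented illustration: 60% of profiles at 0, 25% at 0.25 h, 10% at 0.5 h and 5% at 0.75 h. The mean is 0.0625 + 0.05 + 0.0375 = 0.15 h and the median is 0. A geometric mean computed on the non-zero 40% is exp[(25 ln 0.25 + 10 ln 0.5 + 5 ln 0.75)/40] = 0.34 h.

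**The case against.** The best defence is that the removed values are poorly supported, and much of this stands. SAP 16.1.3 wants the λz regression window to cover at least two half-lives and excludes the tmax point. In the one-compartment model with the protocol's sampling times, every profile above 20% also fails that rule for ka 0.7 to 1.5, and about 66% to 87% fail for ka 3 (CV 30% to 60%). For example, at ka 0.7 the trigger half-life of 4.47 h needs an 8.94 h window. The sampled peak is at 3.0 h, so the longest window is 12 - 3.5 = 8.5 h. Keeping such profiles out of the main t1/2 and AUC0-∞ summaries is therefore defensible. The defence does not reach %AUCextra: a large value there is the finding itself. The SAP also only flags, lists and discusses failures of the span and R² criteria, with no rule that removes them from summaries.

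A reader might infer that sampling failures are concealed. They are not. Individual values are listed, excluded ones are flagged, and n is given for T1, T2, R1 and R2. A shortfall against the n for AUC0-t would be visible, although other reasons for a missing λz could contribute to it.

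A reader might also infer a breach of the protocol's promise of summary statistics. That does not follow: statistics are still given for each endpoint on the evaluable values, and %AUCextra is not itself an endpoint in Protocol 3.

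Nor would tlag be summarised only among profiles with a lag. Mean, median, min and max all include the zeros; only the geometric statistics fail.

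**Conclusion.** The point holds as a minor one. The cap on summarised %AUCextra is certain from the text. The absence of a planned count above 20% is equally plain.

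The shift in the λz-based summaries has a known direction but is conditional on some profile exceeding 20%. In the one-compartment model, geometric mean t1/2 moves by about -1% at an assumed half-life CV of 30% and by -11% to -14% at 60%. Later absorption would make it larger; low variability would make it negligible. It cannot be stated as a fact that t1/2 and AUC0-∞ will be understated by any particular amount.

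A reader might take this as a threat to the bioequivalence conclusion. The documents do not support that: the decision rests on AUC0-t and Cmax, neither of which uses λz. Only descriptive secondary output is affected.

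For tlag, GeoMean, GeoCV% and the 95% CI are undefined as soon as one value is zero, and the SAP gives no handling for that case.

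**What to change.** In SAP 16.1:

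- Delete AUCextra from the parameters set to missing. Summarise %AUCextra on all profiles with a λz estimate, and report the number and percentage above 20% by treatment.
- Keep the summary of λz, t1/2, AUC0-∞, CL/f and Vz/f restricted to profiles at or below 20% as the main one, and add an all-profile row as a supplementary check.
- For tlag, report n, mean, SD, median, min and max, and drop GeoMean, GeoCV% and its 95% CI.

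The cost is a wording change before database lock and a few table rows. The one downside is that the all-profile row includes less reliable extrapolations, so it should be labelled supplementary.
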